15. ASSESSMENT OF SAFETY

Safety for the volunteers is an important prerequisite in planning of clinical trials. According to the Basic Principles mentioned in the World Medical Association (WMA) Declaration of Helsinki^[3], "Every medical research project involving human subjects should be preceded by careful assessment of predictable risks and burdens in comparison with foreseeable benefits to the subject or to others. This does not preclude the participation of healthy volunteers in medical research. The design of all studies should be publicly available."

In drug proving, there is no conventional pharmacodynamic action of the drug, because it is administered in high dilutions, which according to experience provokes transient "proving symptoms", but does not cause toxicological effects. Additionally the administration of the IP usually will last only for a short time, which again minimizes the probability of adverse events. All volunteers will be informed about the objectives, potential risks, inconveniences and benefits of the trial and will sign an informed consent form before the beginning of the trial. All changes on the physical and mental levels will be observed.

For identification of adverse events and their management, the HPCUS guidelines^[9] are being adapted.

15.1 Adverse events

Adverse events (AE) are all unwanted & clinically significant illnesses, diseases, injuries or accidents occurring or worsening in severity during the study period, no matter whether they are causally related to the study intervention or not. The intensity of AE and the causal relationship

with the study interventions have to be assessed and documented. An adverse event, causality of which can be definitely linked to the IPS will be identified as an adverse drug reaction.

To classify as an adverse event, the unexpected symptoms and signs must have at least one of the following characteristics:

- have duration longer than expected
- have clinical severity greater than expected
- have clinical severity that falls within the definition of Serious Adverse Effect
- require therapeutic intervention,
- results in removal from the Proving

All AE that do not meet any of the criteria for serious will be regarded as non-serious events. At the end of the study, any new clinically significant finding/abnormality that meet the definition of an AE will also be recorded and documented as an AE.

15.2 Serious adverse event:

A serious adverse event (SAE) is an adverse event occurring during any phase of the study and at any dose of the IPS or placebo, which fulfils one or more of the following criteria:

- Results in death
- Is immediately life threatening
- Requires in subject hospitalization
- Results in persistent or significant disability or incapacity.
- Medical event that may jeopardize the participant, and may require intervention to prevent one of the serious outcomes noted above.

15.3 Causation likelihood

At each contact with the participant, the investigator will seek information on AE by specific questioning and as appropriate, by examination.

In case of an adverse event, causation likelihood should be determined and would be labeled as:

- 'Possibly related' meaning there is evidence to suggest a 'Reasonable possibility' of a causal relationship between the drug and the adverse event.
- 'Unrelated' meaning there is no evidence to suggest a causal relationship between the IP and the adverse event.

Causation likelihood will be determined prior to un-blinding by the investigator on the basis of

- Temporal relation to IPS administration
- Strength of association
- Consistency over repeated dosing within one subject or across the study population
- Observed increase of symptoms with repetition of dose or increase in attenuation
- Coherence with known facts on the biology of disease

An adverse event must be informed to the CCRH headquarters within 2 working days by telephone/email/fax. A SAE must be informed to the CCRH headquarter within the next 24 hours. The information will be recorded in the Form H. Once AE/SAE is reported to the CCRH headquarters, the principal investigator will identify the participant allocation by un-blinding to re-assess the causality, based upon known biological properties of the substance.

If the causality of the AE/SAE is linked to the IPS, the same would be communicated to the chairperson of the ethical committee and to the site investigator and immediately, along with the follow up course of action.

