9.4.7 Coding/randomization

The UIC of the prover will be used for randomization for:

- Inter- individual control: 30% of the provers will be randomized into placebo group
- Intra-individual control: The drug-placebo sequence will be randomized for each prover in the verum group.

Intra-individual control is proposed to be maintained during the proving process to prevent incorrect attribution of symptoms to the IPS^[7].

The randomization will be done using computerized random number charts for allocation to intervention. This list will be used as the basis for the preparation and labeling of the study medication. Intervention allocation will be concealed until the proving is completed and the database has been locked. The sealed randomization list will be stored by the principal investigator and co-investigator at CCRH headquarters.

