15.4 Un-blinding procedure

Un-blinding of a single participant status will be done by the PI at the headquarters, at his discretion in the event of development of AE/SAE in the prover. The participant allocation will

be informed to the investigator at the study site in case therapeutic intervention required. The code will be accessible only to the concerned investigator and the prover/prover's care giver. The details of any data access including specific personnel who obtained or viewed this information, information that was obtained, date in which it was obtained, and reason for un-blinding will be recorded.

[figure not shown]
Depending on the incidence/severity of AE(s) and its causal relation to the IPS, the PI may opt to un-blind the allocation to entire participants. However, only the allocation for the specific participants will be communicated to the investigator at the study centre.

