16.2 At Headquarters

The study PI will review the original source documents & the data received from the investigators. The PI/Co-I will inform the investigators about the discrepancies in the records. All study related data, reports, meeting minutes, review and assessment records, monitoring records and documents would be kept at one place in the custody of Co-I. The proving data will be entered in the computer and maintained in MS excel formats.

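### Section 15.3 makes the principal investigator unblind every prover with a reported adverse event to re-rate causality, in conflict with 15.4, unreconciled with 9.4.7 and 13.3, and without saying which rating stands

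*Protocol*

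**What the plan says.** Four sections of the protocol govern who may learn a prover's allocation, and when.

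- **15.3, first rating.** The site investigator rates causality blind: "Causation likelihood will be determined prior to un-blinding by the investigator".
- **15.3, second rating.** "Once AE/SAE is reported to the CCRH headquarters, the principal investigator will identify the participant allocation by un-blinding to re-assess the causality". The wording is mandatory, and no limit is set by seriousness, by the first rating or by clinical need.
- **15.4.** Unblinding of a single participant is done by the principal investigator (PI) "at his discretion in the event of development of AE/SAE in the prover". Each access to the code is to be recorded.
- **9.4.7.** "Intervention allocation will be concealed until the proving is completed and the database has been locked". No exception is stated there.
- **13.3.** The PI breaks the codes once the study is complete at the site and the first two phases of data compilation are done. The blinding entry in the study summary also places the code break after the study period at the centre.

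Non-serious events are within the scope of 15.3. Section 15.1 recognises them ("All AE that do not meet any of the criteria for serious will be regarded as non-serious events"), and all events travel to headquarters ("An adverse event must be informed to the CCRH headquarters within 2 working days by telephone/email/fax"). If causality is tied to the IPS, 15.3 has this communicated to the ethics chairperson and to the site investigator.

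**The concern.** Unblinding a prover because that person's care requires it is an ordinary exception to concealment. The stated purpose in 15.3 is different: it opens the code so that causality can be judged again by someone who knows the arm, and it does so for every reported event.

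Three things are at stake. Staff cannot follow a mandatory and a discretionary rule for the same act. Causality ends up with two ratings, one blind and one not, and no rule for choosing between them. And the outcome sent to the site can disclose the arm, because a PI who has seen the allocation will tie an event to the IPS only for a prover who was assigned to receive it.

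**Working it through.** No figure in the protocol bears on this point, so the check is a comparison of the sections.

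**1. Scope of the trigger.** 15.1 divides adverse events into serious and non-serious. 15.3 requires all of them to be reported and attaches the unblinding to the report. Every reported event therefore opens a code.

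**2. 15.3 against 15.4.** Same actor, same act, same trigger. One section says the PI will unblind; the other says the PI may choose. No reading satisfies both, except that the PI always chooses to unblind, which empties the discretion of meaning.

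**3. 15.3 against 9.4.7 and 13.3.** These two sections place the opening of codes at or near the end. 15.3 places it within the reporting cycle of each event, while the proving is running. An un-blinding section can reasonably be read as an exception to a general concealment rule, but neither 9.4.7 nor 13.3 refers to one.

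**4. What the second rating can show.** 15.3 offers two categories, possibly related and unrelated, and both concern a relation to the drug. Under 9.4.9 a placebo-group prover receives placebo in every batch. Let *q* be the share of placebo-group events rated possibly related when blind:

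- blind rating: share related = *q*, which may be any value from 0 to 1;
- rating made knowing the arm: share related = 0, whatever *q* was.

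The placebo group is about 30% of those enrolled, or 0.30 × 40 = 12 provers at the minimum enrolment in 9.3. For these provers the second rating carries no information about how often blind raters suspect the drug when none was given. That background rate is what a placebo group would supply. Under 15.1 an adverse drug reaction needs a definite link to the IPS, so it too becomes impossible in this group once the arm is known.

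**5. Which rating stands.** 15.3 calls the PI's step a re-assessment. Neither 15.3 nor 14.2 says which rating is kept for the record, analysed or reported.

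**6. What reaches the site.** After an unblinded re-assessment, a message that the event is linked to the IPS reveals that the prover is in the verum group. Under 9.4.8 the site investigator is meant to be blind.

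**The case against.** The strongest reply is that 15.3 and 15.4 are safety provisions, that access is logged, and that a dedicated un-blinding section should be read as an exception to 9.4.7. That is a fair reading of 9.4.7 and 13.3. It does not reconcile the mandatory wording of 15.3 with the discretion in 15.4, and it does not settle which rating stands.

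Several stronger inferences are tempting, and the protocol does not support them.

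- *The blind rating is overwritten.* The text says re-assessed. The defect is that precedence is not stated.
- *A planned comparison of related events between arms is biased.* Section 14.2 plans baseline comparisons and the incidence of proving symptoms among those taking the IPS. It specifies no such comparison of related adverse events.
- *The PI's blinding is broken.* 9.4.8 names only site investigators and participants as blind, and 9.4.7 gives the PI and co-investigator custody of the sealed list. The PI also checks the data ("The study PI will review the original source documents & the data received from the investigators"), but the potential to know allocations while doing so exists apart from 15.3.
- *Telling the site contradicts 15.4.* 15.4 releases allocation when therapeutic intervention is required, and 15.5 says such intervention is given for an adverse event. On the protocol's own terms that condition is largely met.
- *Later data from the unblinded prover are coloured.* 15.5 withdraws a prover who has an adverse event, which limits this. Data already collected are kept and remain open to query.
- *People who opened a code must stay out of symptom matching.* 13.3 decodes before matching, and 13.4 segregates symptoms by arm, so matching is unblinded by design for every prover.
- *The number of opened codes measures the bias.* An assumed 10% to 30% event incidence among 40 provers gives 0.10 × 40 = 4 to 0.30 × 40 = 12 opened codes. That counts code breaks, not bias in any result, and the protocol states no incidence.

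**Conclusion.** The point stands as an inconsistency that should be fixed. 15.3 makes unblinding automatic for every reported adverse event, for the purpose of causality rating. This contradicts 15.4 and is not reconciled with 9.4.7 or 13.3. The contradiction with 15.4 depends on no assumption and arises with the first report.

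The consequence for the data is conditional. If the unblinded re-assessment is the rating used, events in placebo-group provers cannot be classed as related, and adverse drug reaction status depends on the arm. If the blind rating is used, this harm disappears; the protocol leaves the choice open. Disclosure to the site arises only for an event that is communicated as linked to the IPS after unblinding, and it concerns that prover only. No planned analysis is shown to be wrong, and no numerical size can be given from the document.

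**What to change.** 1. **Reconcile 9.4.7, 13.3, 15.3 and 15.4** so that one rule says when a code may be opened before database lock.
2. **In 15.3**, remove automatic unblinding for the causality rating of every event and have headquarters re-assess causality blind to allocation. A message to the site then conveys a judgement, not the arm.
3. **Name the rating that counts.** State that the blind rating made before any unblinding is the one analysed and reported by arm.
4. **Keep individual code-breaking under 15.4**, with its access log, and write it into 9.4.7 as an explicit exception.
5. **If allocation-informed review of serious events is wanted for ethics reporting**, keep it, record it separately from the analysed rating, and say whether its outcome goes to the site, since that can disclose the arm.

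The cost is wording in four sections. The blind first rating already exists, so no new assessment is needed. Individual unblinding and an allocation-informed review of serious events both remain available.

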5. ROLES & RESPONSIBILITIES

5.1 Regulatory Committees:

At the level of CCRH headquarters:

The protocol will be placed for approval of:

1. Ethical committee of CCRH
2. Special Committee for Drug Proving of CCRH
3. Scientific Advisory Committee of CCRH

A 'data safety management board' may be constituted by the Director General CCRH for proving of new/non-pharmacopoeial drugs, responsible for supervision of drug proving of new/non-pharmacopoeial drugs.

At each study centre

A Drug proving committee will be formed at each research centre involving faculty from the colleges and scientists at the research centre. The committee shall comprise of 5-6 members responsible for conduct of the study, enrollment & safety of participants, data collection & data integrity, etc.

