5.2 Study Team

At CCRH/Headquarters

Principal Investigator - Director General, Central Council for Research in Homoeopathy, New Delhi

Coordinator & Co-Investigator(s)-Designated officers of CCRH

At Research centre (Centre of CCRH functioning in Homoeopathic Medical College premises)

Site investigator - Designated officer(s) of CCRH responsible for drug proving program

Site co-investigator(s) - Designated officer(s) of homoeopathic college where the proving program is being conducted

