9.4.8 Blinding

The study will be a double blind study, where the site investigators and the participants at the study site will be kept blind about nature of drug substance and the allocation of participants in the verum and placebo groups. The study medication will be sent in coded forms along with a randomization chart. The nature of the proving substance will be known to the PI and the Co-I/coordinator, but the site investigators and the participants will be blind to the nature of the IPS. The coded study medication will be labeled with the UIC and sent to the proving site.

9. 4.9 Interventions

10.3.1 Arms	Assigned Interventions
Group I : IPS	The verum group will be advised to take the study medication as per schedule. This group will comprise of about 70% of the enrolled participants. The IPS will be given in multiple batches, out of which 1 batch will be placebo and other batches will be IP.
Group II: Placebo	The control group will be given placebo indistinguishable from the study medication. This group will comprise of about 30% of the enrolled participants. Multiple batches will be given, all of which will comprise of placebo.

Both the drug and the placebo will be same in appearance, odor and taste.

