17. MONITORING

This study will be monitored periodically by the Director General, CCRH or officers designated by him. The site investigators at the Institute/Unit will allocate adequate time for such monitoring activities. The investigator will also ensure that the monitor or other compliance or quality assurance reviewer is given access to all the above noted study-related documents and study related facilities (e.g. pharmacy, diagnostic laboratory, etc.), and has adequate space to conduct the monitoring visit. Participation as an investigator in this study implies acceptance of potential inspection by CCRH & government regulatory authorities

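### Section 15.3 provides for telling the ethics committee chair only of adverse events linked to the IPS, so notice of serious events on placebo or judged unrelated is not guaranteed

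*Protocol*

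**What the plan says.** Section 15.2 defines an SAE by its outcome, starting with death, and without regard to arm: it is an event "occurring during any phase of the study and at any dose of the IPS or placebo".

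Section 15.3 then sets the reporting route. Sites report any adverse event to headquarters within 2 working days. For serious ones the limit is shorter: "A SAE must be informed to the CCRH headquarter within the next 24 hours". The site investigator judges causality while still blind. Once the report is in, "the principal investigator will identify the participant allocation by un-blinding to re-assess the causality". The sentence that brings in the ethics committee comes directly after this: "If the causality of the AE/SAE is linked to the IPS, the same would be communicated to the chairperson of the ethical committee". It goes on to name the site investigator as a second recipient and to ask that the notice be immediate.

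Four other places bear on who can question the judgement:

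- Section 5.2: "Principal Investigator - Director General, Central Council for Research in Homoeopathy, New Delhi". Section 4 adds that the Council funds the study in full.
- Section 5.1: "A 'data safety management board' may be constituted by the Director General CCRH". This applies only to new or non-pharmacopoeial drugs.
- Section 17: "This study will be monitored periodically by the Director General, CCRH or officers designated by him". Section 17.1 allows independent experts on site visits, as the Director General decides.
- Section 5.4: a general undertaking to follow the national drug law, Good Clinical Practice and the Declaration of Helsinki.

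**The concern.** The protocol collects serious events whatever the arm or cause, then passes them on according to cause. The body meant to look after participants hears of an event only once it has been attributed to the IPS. The protocol places that re-assessment with the head of the sponsoring and funding body, who also decides whether a safety board exists and directs monitoring.

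If the attribution is wrong, the text gives the committee no stated occasion to see the case. Nor does it guarantee the information the committee would need to notice a cluster of serious events, to see harm from trial procedures rather than from the drug, or to compare serious events between arms. These are healthy volunteers, and the protocol is generic and reused from drug to drug, so the gap would recur in each proving.

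**Working it through.** The plan states no figure on this point. The check is a trace of the route, followed by a count for context.

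**1. Route of an SAE under section 15.3**

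| Step | Who | Condition |
|---|---|---|
| Causality judged while blind | Site investigator | none |
| Report to headquarters, 24 hours | Site | none |
| Unblinding and re-assessment | Principal investigator | none in 15.3; discretionary in 15.4 |
| Notice to ethics committee chair | Not stated | causality linked to the IPS |

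Only the last step is conditional. A death in the placebo group meets the definition in 15.2 and reaches headquarters. After unblinding it cannot be linked to the IPS, so the condition fails. A death on IPS that is judged unrelated ends at the same place.

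**2. What counts as linked**

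Section 15.3 uses two labels, possibly related and unrelated. Sections 15.1 and 24.7 reserve the term adverse drug reaction for events definitely linked to the IPS. The notification sentence does not say which level is meant, so the condition may be narrower than possibly related.

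**3. Search for a second route**

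- 5.1: the safety board is optional, limited to some drugs, and has no stated SAE duty. The drug proving committee at each centre is responsible for participant safety, but consists of college faculty and centre scientists.
- 15.4: governs unblinding and informing the site; it does not mention the ethics committee.
- 15.5: covers follow-up of the prover only.
- 17 and 17.1: monitoring directed by the Director General; independent experts possible, with no link to SAEs.
- 18: early termination on the advice of the Council's advisory committees; no SAE route.
- 24.4 to 24.8: definitions only.
- Form G: records causality and the site investigator's signature; no onward recipient.

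None sends an unrelated or placebo SAE to the ethics committee.

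**4. Context: how much planned dosing contains no IPS**

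Inputs: 40 enrolled provers (9.3); 30% on placebo throughout (9.4.7), so 0.30 × 40 = 12 placebo and 28 verum; at least 3 batches (9.4.13). In the verum group there are several batches, "out of which 1 batch will be placebo and other batches will be IP" (9.4.9).

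With k batches per prover, the share without IPS is (12k + 28) / 40k = 0.30 + 0.70/k.

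- k = 3: (36 + 28) / 120 = 64/120 = 53.3%
- k = 4: (48 + 28) / 160 = 76/160 = 47.5%
- k = 5: (60 + 28) / 200 = 88/200 = 44.0%

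With 30 provers and 3 batches the result is the same: (27 + 21) / 90 = 48/90 = 53.3%.

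At k = 3 the 64 batches split into two parts. The 36 in the placebo group (30% of 120) can never be linked to the IPS. The other 28 (23.3%) are placebo batches in verum provers, where a link could be made only through carry-over from an earlier IPS batch.

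**The case against.** The strongest reply is that this argues from silence with part of the document unseen. The adverse-event flow chart in 15.6 is the protocol's own routing diagram and only its heading was available. A figure in 15.4 and the text between 5.2 and 5.4 were also unavailable. Section 5.4 binds the study to Good Clinical Practice, and section 6.1 says provings must conform to it. The notification sentence can be read as an urgent alert for IPS-related events, with a plan of action, and it does not forbid reporting others. It is in the passive and does not name whose assessment triggers notice, and 15.4 leaves unblinding to discretion.

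Much of this stands as a limit on how far the point goes. A reader might infer that serious events on placebo or judged unrelated never receive independent review, or that a wrong causality call cannot be corrected. The documents do not support either statement: a safety board and independent experts are possible, the site makes its own blinded assessment, and the unseen chart may add a step. A reader might also take the 53% as the share of SAEs that would go unreported. It is not. It counts planned batches, whereas dosing lasts 3 days and each washout at least 30, and provers with an adverse event are withdrawn (15.5).

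The reply does not remove the point. A general compliance clause does not say what headquarters must do with a given report, while 15.3 does. The optional bodies may never be convened and have no stated SAE task. If the flow chart shows an unconditional route, it conflicts with the condition in 15.3.

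**Conclusion.** The point holds as a defect in a stated rule. Section 15.3 provides for informing the ethics committee chair only of events linked to the IPS, in a sentence that follows the principal investigator's unblinded re-assessment. The readable text guarantees the committee no notice of other SAEs, deaths included, although 15.2 counts them in both arms.

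Its reach is wide: all dosing in the placebo group, plus any event on IPS that is judged unrelated. The 53% (44% with 5 batches) shows how much of the planned dosing is without IPS and carries no estimate of event numbers, for which the protocol gives no rate. The conclusion assumes that headquarters follows 15.3 as worded and that 15.6 adds no other route. The committee named in 5.1 is the Council's own, so what is at stake is review separate from the principal investigator, not review outside the sponsor.

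**What to change.** In 15.3, replace the conditional sentence with an unconditional one for serious events: every SAE in either arm, whatever the causality judgement, goes from headquarters to the ethics committee chair promptly and within a time limit that the sponsor states. The 24 hours now in 15.3 run from site to headquarters, and the protocol gives no interval for the onward step. Attach the site investigator's blinded causality assessment and let the principal investigator's re-assessment follow. Non-serious events may keep the causality-based route, provided that 15.3 says which causality level triggers it.

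Then check 15.4 and the 15.6 flow chart and reconcile them with the new sentence. This includes the difference between 15.3, where unblinding follows every report, and 15.4, where it is discretionary.

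The cost is a short amendment and a few extra notifications, since SAEs should be rare in about 40 healthy volunteers. The design, sample size and analysis are unaffected.

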13.3 Data compilation

The original source documents i.e. PME, Prover's Day Book Proforma, Symptoms Elaboration Proforma', TME form, case off form, adverse event reporting forms will be sent by investigators from the centres to the coordinators at CCRH headquarters.

Phases of data compilation:

- 1: PME & TME compilation
2. Prover wise entry of symptoms produced(or symptoms not produced) with individual batch
- 3: De-coding & segregation of verum & placebo symptoms
- 4: Analysis & matching of symptoms and compilation of drug pathogenesis

The data base will be prepared by the coordinator at the headquarters. Un-blinding or breaking of the randomization codes will be done by the study PI at the headquarters after the study has been completed at the study site, followed by first & second phase of data compilation.

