15.5 Follow-up of provers after AE (including SAE)

The prover will be withdrawn from the proving in case of development of an AE. Appropriate therapeutic intervention will be given in case of development of an AE. Based on the totality of the presenting symptoms a suitable homoeopathic drug may be chosen on symptom similarity basis and prescribed to the prover. The participant will be provided free treatment for as long as the symptom(s) exist(s).

All unresolved AEs will be followed by the investigator until the events are resolved, stabilized, or the participant is lost to follow up, or the AE is otherwise explained. At the last scheduled visit, the investigator will instruct each participant to report any subsequent events(s) that the participant, believes might reasonably be related to participation in this study.

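### Adverse-event un-blinding (15.3 to 15.5) can reveal a prover's arm to the site investigator who is still rating symptoms in the other provers, against 9.4.7 and 9.4.8

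*Protocol*

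**What the plan says.** Three places set the blind. Section 9.4.7: "Intervention allocation will be concealed until the proving is completed and the database has been locked". Section 9.4.8: "the site investigators and the participants at the study site will be kept blind about nature of drug substance and the allocation of participants". Section 13.3 has the PI break the code "after the study has been completed at the study site, followed by first & second phase of data compilation". None of the three mentions an exception.

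Three places open it:

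- Section 15.3: "Once AE/SAE is reported to the CCRH headquarters, the principal investigator will identify the participant allocation by un-blinding to re-assess the causality". If the event is judged due to the IPS, "the same would be communicated to the chairperson of the ethical committee and to the site investigator and immediately".
- Section 15.4: un-blinding of a single prover is done by the PI "at his discretion in the event of development of AE/SAE in the prover", and the allocation will "be informed to the investigator at the study site in case therapeutic intervention required".
- Section 15.5: the prover is withdrawn, and "Appropriate therapeutic intervention will be given in case of development of an AE".

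Section 9.4.16 gives the investigator three tasks for every prover: questioning about symptoms, classifying each as NS, C-, C+ or RS, and recording a view on causality.

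**The concern.** The site investigator is the measuring instrument in this trial. The outcome is a list of symptoms that this person draws out, words, codes and judges. If that person is told during the trial that a particular reaction came from the IPS, he or she learns what a verum reaction looks like while other provers are still being rated. The same picture can then be probed for more closely, coded more readily as a proving symptom, or more readily called causal.

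The protocol offers a route for this carry-over. Section 15.3 lists consistency across the study population among the grounds for judging AE causality, so one disclosed link can inform the next judgement. Section 14.1.1 counts a symptom as belonging to the remedy with great probability if it meets any one of several criteria, one of which is occurrence in at least two volunteers. One prompted or re-coded symptom in a second prover could meet that criterion.

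**Working it through.** The protocol gives no figure on this point, so there is none to reproduce. The check is a reading of the sections together, with a scale calculation under stated assumptions.

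**Step 1: what triggers un-blinding at headquarters.** Section 15.3 says the PI will un-blind once an AE or SAE is reported, with no threshold of seriousness or need. Section 15.4 leaves un-blinding to the PI's discretion. The two do not agree.

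**Step 2: what reaches the site.**

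| Route | Condition as written | What the site learns |
|---|---|---|
| 15.3 | Event linked to the IPS after un-blinding | The causal verdict, which implies verum; no test of clinical need |
| 15.4 | Therapeutic intervention required | The allocation itself, either arm |
| 15.4 read with 15.5 | 15.5, taken literally, gives intervention for any AE | The 15.4 condition is then met by any AE |

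**Step 3: who receives it.** Sections 15.3 and 15.4 name the site investigator or the investigator at the study site. Section 9.4.16 gives symptom elicitation and classification to the investigator. Section 5.2 allows several investigators and co-investigators per site, but no section keeps the recipient apart from the rater or stops an informed rater from rating others.

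**Step 4: how much rating can follow.** By 11.1, each prover has three batches of 3 days, each followed by at least 30 days of washout: 3 × (3 + 30) = 99 days. Section 9.3 sets 15 to 25 volunteers per centre, so one early disclosure can leave 14 to 24 others under assessment for up to about three months.

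**Step 5: how often the 15.3 route could open.** Take a site of 20, the middle of the 15 to 25 range. With the 70/30 split (section 8), 0.70 × 20 = 14 are on verum. The AE rate per prover, q, is not in the protocol, so it is assumed, with provers treated as independent. The chance of at least one verum AE is 1 − (1 − q)^14:

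| Assumed q | All verum AEs linked to IPS (upper bound) | Half of them linked (assumption) |
|---|---|---|
| 2% | 1 − 0.98^14 = 25% | 1 − 0.99^14 = 13% |
| 5% | 1 − 0.95^14 = 51% | 1 − 0.975^14 = 30% |
| 10% | 1 − 0.90^14 = 77% | 1 − 0.95^14 = 51% |
| 20% | 1 − 0.80^14 = 96% | 1 − 0.90^14 = 77% |

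The middle column is an upper bound because 15.3 informs the site only when the event is also linked to the IPS. Both columns give the chance of a disclosure. Neither measures bias in a result.

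**The case against.** A reader might infer that 15.4 and 15.5 together disclose every AE in either arm, so that site un-blinding is close to certain: 1 − (1 − q)^20 gives 64%, 88% and 99% at 5%, 10% and 20%. The protocol does not support that as settled. Section 15.1 makes the need for treatment only one of five alternative features of an AE, so some AEs may need none and the 15.4 condition can have force. Section 15.5 speaks of appropriate intervention, and 15.4 adds PI discretion, a log of who saw the code and why, and release for the specific prover only. What stands is that 15.5 literally meets the condition, so the wording needs settling.

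A reader might also infer that silence after an AE report tells the site the prover was on placebo or the event was unrelated. That cannot hold together with a claim that every AE is disclosed, and the point does not rest on it.

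Nor does the text show that the resulting symptom picture is made by the rater:

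- The affected prover is withdrawn, and the investigator's own causality call on that event comes before un-blinding (15.3, 15.5).
- The other provers stay masked, so a primed rater would probe both arms. Section 13.4 drops symptoms identical under drug and placebo, so priming could remove a symptom as well as add one.
- Verum and placebo symptoms are separated at headquarters after decoding (13.3), and provers keep their own diary (Form E).
- The multi-prover route to Grade I needs two sites with no contact (14.1.3), which disclosure at one site cannot produce alone.

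These points limit the harm without removing it. The two-volunteer criterion in 14.1.1 has no two-site condition, and the diary does not replace the investigator's elaboration and coding.

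Finally, un-blinding one prover for medical need is ordinary, and site staff have a safety interest in knowing of a linked reaction. Both are right. They bear on who at the site is told, and do not require that person to go on rating. The adverse-event flow charts are not visible in the text at hand and may say more about the route.

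**Conclusion.** The point holds as an indirect threat to rater blinding and as a contradiction in the text. Section 15.3 sends an arm-revealing verdict to the site without tying it to need. Section 15.4 releases allocation under a condition that 15.5 leaves open. Nothing separates the recipient from the rater of the remaining provers, so the promises in 9.4.7 and 9.4.8 are not kept as written.

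Its reach is limited to symptoms recorded by an informed rater after a disclosure, and mainly to criteria that a single site can satisfy. The 25% to 96% range rests on assumed AE rates, a 20-prover site and independence between provers. It bounds how often the 15.3 route could open and says nothing about the size of any bias. The change is worth making because no analysis can re-blind a rater afterwards.

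**What to change.** 1. Reconcile 15.3, 15.4 and 15.5 with one another and with 9.4.7, 9.4.8 and 13.3. In particular, settle whether un-blinding on an AE is automatic or discretionary, what the 15.4 condition means given 15.5, and that the concealment statements carry this exception.
2. Route any allocation, or any causality verdict that reveals it, to a designated person at the site who does not elicit or classify symptoms. Where an investigator has already been told, have an uninformed site co-investigator (5.2) record and classify symptoms in the remaining provers.
3. Add to the access log that 15.4 already requires the date on which each symptom rater was informed. Repeat the symptom compilation leaving out symptoms recorded at that site by an informed rater after that date, and report whether any symptom changes status.

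The cost is a few sentences and some reallocation of work among existing site staff. What safety information the site holds, and how the affected prover is cared for, stay as the sponsor determines.
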